Official Title: Is the Rehabilitation Robotic a Safe and Effective
Choice for Stroke Patients?

NCT number: not-yet assigned

Date of the document: September 20th, 2017

Introduction

The number of incident strokes, prevalent stroke survivors, disability-adjusted life-years (DALYs) lost due to stroke, and stroke-related deaths is increasing in the world (1). Stroke is the most common cause of complex disability in Taiwan (2). After the acute phase of stroke, many patients are left with impairment of upper-limb movement (hemiparesis) because of the hand weakness and abnormal contractions. Motor recovery of the hand is the slowest and most difficult, leading to limited hand activities and occupational disability. Therefore, facilitating motor recovery of hand after stroke is crucial in stroke rehabilitation.

The mechanisms of recovery after stroke are multifactorial and the effect of rehabilitation programs is complex (3). Activity-dependent neural plasticity of the cortical maps adjacent to the lesion probably occurs, particularly during the acute period after stroke (4). In order to stimulate such plasticity, many new rehabilitation methods, including rehabilitation robots, have been developed according to the principles of motor learning (5). Robotic systems can provide repetitive, reproducible, interactive forms of physical therapy that can be quantified (6). The advantages of using robots in neuromotor rehabilitation includes favoring attention and reducing the effort of the patient during training (7), boosting motivation and adherence to treatment (8), as well as help in multi-sensory and sensorimotor integration (9). Some results are very promising, showing that robot-assisted therapy is safe and well tolerated and that it has a positive impact on muscle strength and function in the paretic arm (10-12). However, the quality of these evidence is still controversial and inconclusive. The effectiveness of robotic over conventional therapy is arguable and the best therapy strategy is still not clear. Furthermore, there is little understanding of the neurological mechanisms involved in functional recovery of the hand (13). In this study, the investigators hypothesize that the

robot based assistance would outperform conventional therapy during the subacute stage of stroke.

Study objective

1. To establish whether robot assisted therapy provides any additional motor recovery for the hand when administered during the subacute stage in a Chinese adult population diagnosed with stroke.
2. To evaluate the feasibility and efficacy of robot-assisted hand rehabilitation in improving arm function abilities in subacute hemiplegic patients.

Outcome evaluation

(A) Fugl-Meyer assessment (FMA) scale (14): The investigators used FMA scale to evaluate sensorimotor recovery of patients with particular attention to the hand and wrist section (maximum score=24) to assess the functional capacity of the affected hand.

(B) The Motricity Index (MI) scale (15): The investigators used MI scale to assess the motor recovery rate of the patients (100% = maximum MI).

(C) Functional Independence Measure scale (FIM) (16): The investigators used FIM to assess the degree of independence and need-of-assistance in basic activities of daily living at enrolment and at the end of the study. FIM is an 18-item ordinal scale rated from 1 (total dependence) to 7 (total independence) per item; 13 items of this scale, the sub-scale Motor- FIM, were used to evaluate motor disability.

(D) Visual analogue scale (VAS) (17): The investigators used VAS (0 extremely simple- 10 extremely difficult) to assess the feasibility of the device in terms of the number of patients who completed the program; side effects (the physiotherapist was required to report any adverse events occurring during the study in regard to the use of the robotic hand); and the level of operator difficulty for the physiotherapist in managing the device.

Intervention

The experimental group will receive 30 minutes robotic training sessions, 3 times per week for a total of 30 sessions supervised by a research assistant. The robotic hand is a passive exoskeleton system, which was developed by the laboratory of the Department of Biomedical Engineering in Chung-Yuan Christian University. Participants will be placed in the robot and practice common hand tasks involving single finger range of motion exercise, grasping, and pinching objects. Immediately following this robot training, these subjects will receive schedule (1-hour sessions, 3 times/week, 30 total sessions) of conventional

[figure not shown]
therapy from an occupational therapist. An occupational therapist will provide one-on-one individualized programs focused on arm and hand function. Treatment will include function-oriented specific tasks, such as reach, grasp, transport and release of various objects between different targets.

In conventional therapy group, participants will receive an one-hour of one-on-one treatment from an occupational therapist, focusing on arm and hand function. Treatment will include function-oriented specific tasks, such as reach, grasp, transport and release of various objects between different targets. The treatment schedule will parallel that given to the experimental group (1-hour sessions, 3 times/week, 30 total sessions). All patients would undergo basic rehabilitation following the guidelines (18) according to the Bobath concept (19).

Statistical analysis

Statistical analysis was performed with SPSS 22.0 (IBM, USA). The normality of variables was assessed using the Kolmogorov–Smirnov test. Confirmation of matching in initial conditions in co-factors among control and intervention groups was made using Wilcoxon Rank Sum (WRS) tests with continuity correction or Fisher’s exact test (FET), depending on the nature of the variables (categorical, interval or ratio). For each group, improvements in dexterity performance were evaluated using Wilcoxon Sign Rank (WSR) test with continuity correction for paired samples. Comparative differences between control and intervention in these improvements were established using Wilcoxon Rank Sum tests with continuity correction. Cohen’s d effect sizes and the 95% confidence interval for the contrast (continuous data) were further calculated. In all cases, statistical significance threshold was kept at $\alpha = 5\%$.

Steps of experiment

Study participants

(A) Inclusion criteria: Adult patients (>20 years old) with a diagnosis of hemorrhagic or ischemic stroke and who experience severe upper extremity hemiparesis.

(B) Exclusion criteria: severe pain and instability in the wrist of the affected arm, severe cognitive impairment, aphasia, hemispatial neglect, apraxia and joint contractures greater than 20 degrees in the affected hand.

(C) The number of estimated enrollment is thirty-six stroke patients (18 in intervention group and 18 in control control).

References

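### The title asks whether the robot is safe, but the only adverse-event collection described is of device-attributed events, with none described for the control arm, so added harm over conventional therapy cannot be judged

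*Combined protocol and SAP*

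**What the plan says.** All references are to the combined protocol and SAP.

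- **Official Title.** It poses safety as a question alongside efficacy: "Is the Rehabilitation Robotic a Safe and Effective" choice for stroke patients.
- **Introduction.** It cites results "showing that robot-assisted therapy is safe and well tolerated", then says that "the quality of these evidence is still controversial and inconclusive".
- **Study objective.** The first objective concerns motor recovery of the hand. The second is "To evaluate the feasibility and efficacy of robot-assisted hand rehabilitation in improving arm function abilities". Neither names safety.
- **Outcome evaluation (D).** Side effects are listed as one component of device feasibility, with programme completion and operator difficulty. The collection rule is that "the physiotherapist was required to report any adverse events occurring during the study in regard to the use of the robotic hand". No other adverse-event text appears in the document.
- **Intervention.** The robot arm has 30-minute robot sessions, "3 times per week for a total of 30 sessions supervised by a research assistant", each followed immediately by one hour of conventional therapy from an occupational therapist. The control arm has the same conventional therapy without the robot. All patients also have basic rehabilitation, whose hours are not given.
- **Statistical analysis.** Baseline comparability and improvements are covered. No adverse-event summary or comparison is described.

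**The concern.** Two features of the reporting rule limit what the trial can say about safety.

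First, an event is reportable only if it concerns use of the robotic hand, so somebody has to judge cause before anything is written down. That judgement is difficult here. Robot training and conventional hand therapy follow one another directly and both include grasping with the affected hand. If an event is wrongly judged unrelated to the robot, the plan describes no other route by which it would be recorded.

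Second, control patients do not use the robot, so by the rule's wording they cannot produce a reportable event, and no other collection is described for them. Patients in either arm may have events from the stroke or from the therapy that both arms receive. The control arm is the trial's only internal source for that background, and the plan does not describe using it.

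What is at stake is how far the title's question can be answered. The efficacy results are untouched.

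**Working it through.** **The plan's own figures.** Enrolment is 18 + 18 = 36 (Study participants, item C). The plan gives no event rate, so every event count or rate below is an assumption. The conclusion itself rests on the wording and not on any of these numbers.

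**What the wording yields**

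| | Robot arm | Control arm |
|---|---|---|
| Event attributed to the robot | reported | cannot arise |
| Event not attributed to the robot | no collection described | no collection described |

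One of the four cells is filled. A device-attributed count in the robot arm can be described, but there is nothing to set it against.

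**What the fix would show (assumed all-cause counts).** The current plan would not produce these counts. They illustrate what recording all events in both arms would add. Suppose 4 of 18 robot patients have at least one event of any cause: 4/18 = 22%, exact (Clopper-Pearson) 95% CI 6.4 to 47.6%. The differences below have exact unconditional 95% intervals (score statistic, two one-sided 2.5% tests).

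| Control patients with an event (assumed) | Difference, robot minus control | 95% CI | Two-sided Fisher p |
|---|---|---|---|
| 4/18 | 0 points | -29 to +29 | - |
| 2/18 | +11 points | -16 to +39 | 0.66 |
| 0/18 | +22 points | +2 to +48 | 0.10 |

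Without a control count, these three readings of the same 4/18 cannot be told apart. In the last row the interval excludes zero while Fisher's test does not reach 0.05. This is not a contradiction: Fisher's test is conditional on the total number of events and is more conservative. By Fisher's test, at least 5/18 v 0/18 is needed for p ≤ 0.05.

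**What 18 per arm cannot do**

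- No events in 18: upper two-sided 95% limit = 1 - 0.025^(1/18) = 0.185, or 18.5%.
- No events in either arm: difference -18.4 to +18.4 points.
- Exact power of a two-sided 5% Fisher test for assumed control v robot rates: 5% v 20%, 13%; 10% v 30%, 20%; 10% v 40%, 43%.

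**Why collection must be the same in both arms.** Scheduled session time is 30 × 0.5 h + 30 × 1 h = 45 h in the robot arm and 30 × 1 h = 30 h in the control arm, a ratio of 1.5. If control-arm collection were added but staff noted only what they saw during sessions, an equal hourly rate would give a robot-arm rate of 1 - (1 - c)^1.5 for a control rate c:

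- c = 10%: 14.6%, a spurious gap of 5 points
- c = 20%: 28.4%, a gap of 8 points
- c = 40%: 53.5%, a gap of 14 points (13.5)

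These gaps are upper values for that scenario, because the basic rehabilitation hours are not stated and would shrink the ratio if also observed. With an assumed 30 further hours per arm it is 75/60 = 1.25, and 20% becomes 1 - 0.8^1.25 = 24%. This is a reason to ask about the whole period since the last visit. It is not a defect of the present plan.

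**The case against.** The strongest reply is that nothing the plan promises fails. The objectives name motor recovery, feasibility and efficacy; the hypothesis is about outperforming conventional therapy; and the only between-arm outcome contrast is in improvements. The title asks whether the robot is safe, not whether it is safer than or as safe as conventional therapy. Side effects sit within device feasibility, and for that purpose device-attributed events in the robot arm are a proper measure. All of this stands. A reader might infer that a stated safety objective goes unmet, and the documents do not support that: the gap is between the title's question and the data collection described.

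A reader might also infer that all other adverse events go unrecorded. The documents do not say so. They describe no other collection, which is a narrower statement.

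It is also fair that the full fix gains limited precision, and that limiting the safety conclusion resolves the mismatch by wording alone. Both points bear on the strength of the recommendation. They do not remove the filter on attribution before recording, or the lack of any described control-arm events.

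**Conclusion.** The point holds in limited form. As written, the trial can describe device-attributed events in up to 18 robot patients. It cannot say whether adding the robot to conventional therapy adds harm, and it may miss events wrongly judged unrelated. This rests on reading the phrase about use of the robotic hand as restricting what is reported. Even if that phrase is read broadly, no control-arm collection is described.

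The plan gives no event rates, so the size of any missed harm cannot be estimated. A reader might take the fix to make this a test of comparative safety; at 18 per arm it would not, as the limits shown above make clear. The improvement is worthwhile and inexpensive, and no efficacy result depends on it.

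**What to change.** **Preferred.** Record all adverse events in both arms, using:

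- the same form and the same standard question, covering the period since the last visit;
- the same window, from enrolment to the end-of-study assessment (FIM already has assessments "at enrolment and at the end of the study"), including patients who stop early;
- the same existing staff role in both arms, for example the occupational therapist, who is described as treating both groups;
- relation to the device as a separate field, completed after the event is recorded.

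Report patients with at least one event per arm and the difference, descriptively, with exact 95% CIs. State that the contrast is robot sessions added to conventional therapy, and that 18 per arm cannot establish comparative safety.

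**Otherwise.** If control-arm events are not collected, limit the safety conclusion to device-attributed events in the robot arm. This costs only a change of wording.

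**Cost of the preferred route.** One short question at existing visits, at most 30 × 36 = 1,080 entries over 30/3 = 10 weeks of sessions per patient, plus one end-of-study contact for patients who stop early and a few lines of text. The downsides are slightly more data entry, a reporter who knows the arm, and an imprecise comparison.

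**Separate drafting points, which add no weight to the above.** The physiotherapist is named as reporter and device operator, while a research assistant supervises the robot sessions; these statements should be reconciled. Completion and adverse events are listed under a VAS that suits only "the level of operator difficulty for the physiotherapist in managing the device", so the three should be listed as separate measures.

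### Outcome (D) limits adverse-event reports to events connected with the robotic hand, so it gives no control-arm count and may leave out some robot-arm events

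*Combined protocol and SAP*

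**What the plan says.** The title opens "Is the Rehabilitation Robotic a Safe and Effective" and so puts safety beside efficacy. The Introduction cites favourable results on the safety and tolerability of robot therapy, then says that "the quality of these evidence is still controversial and inconclusive". The Study objective section names motor recovery, feasibility and efficacy, but not safety.

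Harms appear once, in Outcome evaluation (D), as one of three parts of device feasibility. The other two are the number of patients who complete the programme and "the level of operator difficulty for the physiotherapist in managing the device". The harms part reads: "the physiotherapist was required to report any adverse events occurring during the study in regard to the use of the robotic hand".

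Under Intervention, robot sessions run "3 times per week for a total of 30 sessions supervised by a research assistant". Then: "Immediately following this robot training, these subjects will receive schedule", which introduces 30 one-hour sessions of conventional therapy from an occupational therapist. In the control arm, "participants will receive an one-hour of one-on-one treatment from an occupational therapist", and "The treatment schedule will parallel that given to the experimental group". All patients also receive basic rehabilitation on the Bobath concept, for a time that is not stated.

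The Statistical analysis section compares improvements between arms and uses Fisher's exact test only for baseline matching. It describes no analysis of adverse events.

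**The concern.** The reporting rule is tied to use of the device, and this has two consequences. First, a patient who never uses the device cannot have a reportable event, so the control arm contributes nothing. Yet control patients attend the same number of occupational therapy sessions on the same schedule, and they are the natural reference for how often a hemiparetic hand becomes sore or stiff during therapy alone. Second, a robot patient whose wrist pain is put down to the following hour of therapy, or to basic rehabilitation, may not be reported.

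What is at stake is how a low count can be read. Few reports could mean few events, or events assigned to another cause, and no control figure would help a reader tell these apart. A paper under this title would be expected to comment on safety, and events not recorded at the time may not be recoverable later.

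**Working it through.** The point rests mainly on the text. The plan states no safety figure that could be reproduced. The event rates and logging times below are assumptions.

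**1. Scope of the rule against exposure**

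| | Robot arm | Control arm |
|---|---|---|
| Robot training | 30 × 0.5 h = 15 h | none |
| Occupational therapy | 30 × 1 h = 30 h | 30 × 1 h = 30 h |
| Basic rehabilitation | given, hours not stated | given, hours not stated |
| Event within the reporting rule | if connected with the robot | cannot arise |

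Robot training is 15/45 = 33% of robot plus occupational therapy time. Basic rehabilitation adds an unknown amount to the denominator, so 33% is an upper limit on the robot's share of all therapy. The sessions run over 30/3 = 10 weeks.

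**2. Who is present.** A research assistant supervises the robot sessions, and an occupational therapist gives the conventional sessions in both arms. The physiotherapist is described as managing the device and is the only role with a stated duty to report.

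**3. What a count out of 18 can show.** Exact (Clopper-Pearson) two-sided 95% intervals:
- 0 of 18: 0 to 1 − 0.025^(1/18) = 18.5%
- 3 of 18: 3.6% to 41.4%

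If, purely for illustration, 3 robot patients had a hand or wrist event, the reported count could lie anywhere from 0 to 3 according to how the events were classified. This follows from the assumption and is not evidence of how often misclassification would occur.

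**4. Whether a both-arm count could be tested.** With no control events, the two-sided Fisher p-value for 5 of 18 robot patients is 2 × C(18,5)/C(36,5) = 2 × 8,568/376,992 = 0.045. For 4 of 18 it is 0.104, so 5 is the smallest significant count. The plan does not say whether its 5% level is one- or two-sided; two-sided is assumed here.

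| Assumed rates, control v robot | Exact Fisher power | Chance that robot count is no higher than control count |
|---|---|---|
| 5% v 15% | 5% | 23% |
| 5% v 20% | 13% | 12% |

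A both-arm count is therefore descriptive only.

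**5. Equal ascertainment.** A question at each occupational therapy session gives every patient 30 occasions for detection. Adding events noticed at robot sessions would give the robot arm 30 + 30 = 60 occasions against 30, and would inflate its count. The by-arm figure must come from the common question alone.

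**6. Cost.** 36 × 30 = 1,080 entries. At 15 seconds each, 16,200 s = 4.5 h; at 60 seconds each, 64,800 s = 18 h. Per patient this is 7.5 to 30 minutes.

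**The case against.** The strongest reply is that the rule suits its stated purpose. Side effects are collected to judge the feasibility of a device, and device-related events are a defensible choice for that. Neither objective names safety, so the case for a comparative count leans on the title. This stands, and it sets the weight of the point. It does not remove it, because the title invites a safety conclusion that the collection cannot support.

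Three stronger readings are tempting, and the documents do not support them:
- *The reporter must first decide that the robot caused the event.* The wording links events to use of the robot but does not demand proof of cause. A generous reporter could include anything arising around robot use. The fair statement is that some robot-arm events may be left out.
- *The wrong person reports, and those who see the hand do not.* One reporter is named and nobody is excluded. The research assistant and the physiotherapist may be the same person, and the physiotherapist is treated as the device operator.
- *Tolerability goes unmeasured.* Outcome (D) also counts patients who complete the programme, and that needs no attribution. It is a coarse signal, since a patient can finish with a painful wrist.

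It is also fair to say that 18 per arm cannot compare rates usefully, that staff know who used the robot, and that any excess would partly reflect 15 extra hours of hand training. All of this stands. It argues against a test, not against counting.

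**Conclusion.** The point holds as a cheap improvement that should be made. As written, the rule cannot produce a control-arm count, because control patients have no robot use to which an event could relate. It may also omit robot-arm events put down to the adjoining therapy or to basic rehabilitation. The number of events that would be lost cannot be estimated from the documents. A reader might infer that the plan ignores harms or contradicts its own objectives. Neither follows, since device-related events are collected and safety is not a stated objective. A reader might also infer that a both-arm count would settle whether the robot is safe. It would not: at the assumed rates, power is 5% to 13%. The gain is a reference figure for description. The conclusion rests on reading the clause in Outcome (D) as the whole of the harms collection, since no other provision is described.

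**What to change.** Keep the physiotherapist's device-related report as part of feasibility, and add the following.

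- At each occupational therapy session, ask every patient in both arms one standard question about new or worse hand or wrist problems, including pain and loss of joint range. Record every positive answer whatever the suspected cause, with relation to the device as a separate field.
- Report by arm the number of patients with at least one event found by that question, out of all who started treatment, with exact 95% confidence intervals and no test.
- List separately the events seen only at robot sessions or elsewhere, with their source, and the subset judged device-related. Do not add these separately found events to the by-arm count.

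The cost is 4.5 to 18 staff hours over the whole trial at the assumed 15 to 60 seconds per entry, plus a short log form and brief staff training. Sample size, treatment and the efficacy analysis do not change. The report should state that the comparison is descriptive, that staff knew who used the robot, and that the robot arm had 15 more hours of hand training.

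### The between-group test on change uses no baseline covariate, and baseline significance tests at 18 per arm cannot confirm matching; prespecify a rank-based comparison adjusted for baseline

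*Combined protocol and SAP*

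**What the plan says.** The Statistical analysis section uses baseline in two ways. It tests comparability: "Confirmation of matching in initial conditions in co-factors among control and intervention groups was made using Wilcoxon Rank Sum (WRS) tests", with Fisher's exact test for categorical variables. It also subtracts baseline to form improvements. Within each arm, "improvements in dexterity performance were evaluated using Wilcoxon Sign Rank (WSR) test with continuity correction for paired samples". Between arms, "Comparative differences between control and intervention in these improvements were established using Wilcoxon Rank Sum tests with continuity correction". Cohen's d is added: "effect sizes and the 95% confidence interval for the contrast (continuous data) were further calculated". Everything is judged at 5%. No section contains a baseline-adjusted model or says which of these analyses is the main one.

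The improvements being compared are described as dexterity, a label that none of the four listed outcomes (FMA, MI, FIM, VAS) carries. Timing is explicit only for FIM, which is scored "in basic activities of daily living at enrolment and at the end of the study". For FMA and MI an enrolment score can be inferred only if the paired tests are meant to cover them.

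On size, the Study participants section says "The number of estimated enrollment is thirty-six stroke patients", 18 per group. The population is patients "who experience severe upper extremity hemiparesis", and the FMA is used "with particular attention to the hand and wrist section (maximum score=24" points), so it is a bounded scale on which low starting scores are plausible.

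**The concern.** Comparing raw change fixes the coefficient of baseline at 1, and the plan gives no reason to expect that value. If the true slope of end score on baseline is below 1, change scores carry avoidable noise, and an arm that happens to start worse gains an apparent advantage. The plan's only safeguard is the set of baseline tests. In a trial this small a non-significant result says little about balance, and the plan does not say what follows from a significant one. At stake are power in a 36-patient trial and the credibility of the contrast if the arms differ at the start.

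**Working it through.** **Inputs from the documents.** 18 per arm; 5% level (two-sided assumed); rank-sum test on change with continuity correction; FMA hand and wrist section bounded at 24. The enrolment of 36 cannot be reproduced, because no effect size, SD, power or dropout is given.

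**Assumptions.** Baseline-to-end correlation rho of 0.3, 0.5 and 0.7; effect of 0.8 end-score SD; end SD equal to, or 1.4 times, baseline SD. Simulations used 20,000 trials per scenario. The adjusted test is a linear model of rank(change) on group and rank(baseline), with 33 df.

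**Step 1: can the baseline tests confirm matching?** Under random allocation the SE of the baseline difference is sqrt(2/18) = 0.333 SD. P(|difference| >= 0.5 SD) = 2 × (1 − Phi(0.5/0.333)) = 2 × (1 − Phi(1.5)) = 0.134. By simulation the planned rank-sum test is non-significant in about two thirds of those trials. It detects a true 0.5 SD difference 28.7% of the time (a t-test, 31%).

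**Step 2: what does change lose to adjustment?** Let k be end SD divided by baseline SD. The slope is rho × k. For linear estimators the change variance is 1 + k² − 2 × rho × k and the adjusted variance is k² × (1 − rho²), in units of baseline variance. A 0.5 SD baseline gap biases the change contrast by (1 − slope) × 0.5 baseline SD.

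| | rho 0.3 | rho 0.5 | rho 0.7 |
|---|---|---|---|
| k = 1: slope | 0.30 | 0.50 | 0.70 |
| bias at 0.5 SD gap | 0.35 | 0.25 | 0.15 |
| adjusted/change variance | 0.91/1.40 = 0.65 | 0.75/1.00 = 0.75 | 0.51/0.60 = 0.85 |
| power, planned | 47% | 61% | 83% |
| power, rank-adjusted | 63% | 72% | 87% |
| k = 1.4: slope | 0.42 | 0.70 | 0.98 |
| bias at 0.5 SD gap | 0.29 | 0.15 | 0.01 |
| adjusted/change variance | 1.78/2.12 = 0.84 | 1.47/1.56 = 0.94 | 1.00/1.00 = 1.00 |
| power, planned | 57% | 71% | 88% |
| power, rank-adjusted | 64% | 73% | 88% |

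On a rounded and clipped 0-24 scale with equal latent SDs, power is 52/65/84% planned against 64/72/86% adjusted.

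**Step 3: type I error.** Over all randomisations the planned test rejects 4.4 to 5.0% and the rank-adjusted test 4.6 to 5.4%. With a realised 0.5 SD gap, no true effect and equal SDs, the planned test rejects 8.3/7.7/6.5% (0-24 scale: 7.7/6.4/5.8%). With k = 1.4 it rejects 6.7/5.7/4.7%. The adjusted test at such gaps rejects 4.8 to 5.7%.

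**Step 4: where adjustment does not help.** With skewed (lognormal) gains and slope near 1, power is 61% for both rank tests. With responder mixtures it is 44% for both in one setting and 36% for both in another. With 55 to 80% of patients at the baseline floor, the gain is 0 to 6 points.

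**Step 5: should a linear model decide instead?** With normal data linear ANCOVA gives 67/75/89% at k = 1, which is 4, 3 and 2 points above the rank-adjusted test. In the skewed scenarios it gives 53 to 54% against 61%. In the responder mixtures it gives 34% against 44% and 26% against 36%. For a constant shift on skewed gains it gives 19 to 44%, against 48 to 77% for the rank-adjusted test.

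**Step 6: checks on the reporting options.** A percentile bootstrap interval for the adjusted difference covered 92.2 to 92.6% in separate runs; the model's t interval covered 95.0%. A proportional-odds likelihood-ratio test with baseline as covariate rejected 6.5% under the null on the 0-24 scale (rho 0.5, 5,000 trials), where the planned test rejects 4.7%.

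**The case against.** The strongest reply is that the planned test is valid under random allocation, that ranks suit bounded scales in severely affected patients, and that the remaining argument is about efficiency. The large gains need a low correlation and equal SDs. Nothing in the documents places this trial there, and in the floor, skew and responder settings that are plausible here the gain is small or nil. All of that stands. It limits the size of the point but does not remove it: in the scenarios run for this test the loss from adjusting was at most about half a point, against gains of up to 16. That range describes the scenarios chosen and is not a bound. A related method that ranks end scores lost 1 to 2 points at rho 0.85, and at rho 0.7 on a bounded scale.

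Three stronger readings are tempting, and the documents do not support them:
- **The planned test is invalid or inflates type I error.** It does not under random allocation. The excess appears only in trials that happen to be imbalanced.
- **Ranks are the mistake and linear ANCOVA should decide.** The severe population and bounded scale make floors and skew plausible, and there the linear test can lose substantial power.
- **Adjustment would repair a non-random allocation.** The plan is silent on allocation, which does not show that it is non-random. If it were, adjustment would reduce confounding but not remove it.

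It is also fair to say that the paired tests name only dexterity, so an enrolment score for FMA and MI is an inference. The fix therefore asks for it to be stated.

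**Conclusion.** The point holds as a recommended, inexpensive improvement and not as a finding of an invalid analysis. Two parts do not depend on an assumed correlation: non-significant baseline tests at 18 per arm cannot confirm matching, and the plan does not say which scales its between-group comparison covers. The benefit of adjustment does depend on assumptions that the documents cannot settle. For an effect of 0.8 end SD and normal data it is about 16, 11 and 4 points of power at rho 0.3, 0.5 and 0.7 with equal SDs, 7, 2 and 0 points with end SD 1.4 times baseline, and about zero with skewed gains and slope near 1. Protection in an imbalanced trial is modest: at a 0.5 SD gap with equal SDs, about 6 to 8% false positives for the planned test against about 5% when adjusted. Confidence is medium, because the correlation, SDs and distributions are unknown.

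**What to change.** In the Statistical analysis section:

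1. State which listed scales the comparison of improvements covers (for example FMA hand and wrist, MI, Motor-FIM), and that each is scored at enrolment as well as at the end.
2. For each such scale, name as the main between-group test a linear model of the rank of change on group and the rank of baseline on the same scale, at the plan's 5% level. Apply it regardless of what the baseline table or the normality check shows.
3. Report the baseline-adjusted difference in scale points from a linear model of end score on group and baseline, with its t-based 95% interval or a permutation-based interval. Do not use a percentile bootstrap. State that the rank-adjusted test decides if the two disagree.
4. Do not offer a proportional-odds model as an alternative at this sample size.
5. Keep the planned rank-sum test on change as a sensitivity analysis.
6. Replace the matching tests with a descriptive baseline table.

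The cost is SAP wording, a ranking step and a linear model in the SPSS version already named; no extra patients are needed. The downsides are little or no gain when the baseline slope is near 1, up to about 5 points less power than linear ANCOVA with normal data, and a p-value and interval that come from different models, hence the stated rule. Choice of a primary scale, multiplicity and the method of allocation are separate points that this change does not settle.
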